12.1.3 Additional Requirements for Healthy Subjects

1. Healthy adult male and female subjects will be matched 1:1 to at least one specific subject in the renally impaired cohorts based upon age, BMI, and sex. The following criteria should be fulfilled:
 - Age must be within \pm 10 years of the matched subject(s)' age in the renally impaired cohort.
 - BMI must be within \pm 20% of the matched subject(s)' BMI in the renally impaired cohort.
2. Continuous non-smoker who has not used nicotine/tobacco containing products for at least 3 months prior to the first dosing and through EOT or ET.
3. Baseline eGFR \geq 90 mL/min/1.73 m² at Screening based on the MDRD equation as described in [Section 12.1.2](#) (Criterion 4). Based on the discretion of the PI or designee, a single assessment of actual creatinine clearance evaluated over a 24-hour urine collection may be used in place of the eGFR (based on the MDRD) equation for healthy subjects. Individual eGFR values recorded for each measurement contributing to the subject mean baseline value must fall within the specified eGFR range for a healthy matched subject (\geq 90 mL/min/1.73m²).
4. Medically healthy with no clinically significant medical history, physical examination, laboratory profiles, vital signs or ECGs, at Screening and at the time of Check-in (Day -1), as deemed by the PI or designee, and as confirmed by the Celerion Medical Monitor and the Sponsor.
5. Liver function tests (ALT and AST), serum (total and direct) bilirubin, amylase, and lipase must be within the upper limit of normal for the laboratory used by the CRU at Screening and Check-in (Day -1). Rechecks of the LFTs (ALT and AST), serum (total and direct) bilirubin, amylase and lipase will be permitted up to 2 times to confirm subject eligibility. Subjects may be eligible for participation in the study based on rechecked values if these values are within normal ranges and if the PI (or designee), with agreement from the Celerion Medical Monitor and the Sponsor, feels that the results are not clinically significant, and will not impact study conduct.

12.2 Exclusion Criteria

Subjects must not be enrolled in the study if they meet any of the following criteria:

12.2.1 All Subjects:

1. Mentally or legally incapacitated or has significant emotional problems at the time of the screening visit or expected during the conduct of the study.

2. History or presence of clinically significant medical or psychiatric condition or disease in the opinion of the PI or designee, and as confirmed by the Celerion Medical Monitor and the Sponsor.
3. History of any illness that, in the opinion of the PI or designee, and as confirmed by the Celerion Medical Monitor and the Sponsor, might confound the results of the study or poses an additional risk to the subject by their participation in the study.
4. History of stomach, or intestinal surgery, or resection, gastritis, gastrointestinal tract, or hepatic disorder or other clinical condition that might, as deemed by the PI (or designee) with agreement from the Celerion Medical Monitor and the Sponsor, affect the absorption, distribution, biotransformation, or excretion of LOXO-292 (appendectomy, hernia repair, and cholecystectomy will be allowed, bariatric surgery will not be allowed).
5. Subject has required treatment for gastrointestinal bleeding within 6 months prior to Check-in (Day -1).
6. History or presence of alcoholism or drug abuse within the past 2 years prior to dosing.
7. History or presence of hypersensitivity or idiosyncratic reaction to the study drugs or related compounds, or inactive ingredients.
8. History or presence of:
 - liver disease,
 - pancreatitis,
 - peptic ulcer disease,
 - intestinal malabsorption,
 - gastric reduction surgery,
 - unexplained syncope,
 - history or presence of clinically significant cardiovascular disease:
 - myocardial infarction or cerebrovascular thromboembolism within 6 months prior to dosing
 - symptomatic angina pectoris within 6 months prior to dosing
 - New York Heart Association Class ≥ 2 congestive heart failure within 6 months prior to dosing
 - congenital prolonged QT syndrome
 - ventricular pre-excitation syndrome (Wolff-Parkinson White syndrome)
 - arrhythmia or history of arrhythmia requiring medical intervention
 - ventricular dysfunction or risk factors for Torsades de Pointes (e.g., heart failure, cardiomyopathy, family history of Long QT Syndrome)

- significant screening ECG abnormalities:
 - Left Bundle branch block
 - Second degree atrioventricular (AV) block, type 2, or third degree AV block

9. Female subjects of childbearing potential.

10. Female subjects with a positive pregnancy test or who are lactating.

11. Subjects with at-rest (i.e., supine for at least 10 minutes) heart rate lower than 45 bpm or higher than 99 bpm at Screening, Check-in (Day -1), and prior to dosing. Out-of-range values that are not clinically significant (as determined by the PI or designee) may be repeated twice during Screening, Check-in (Day -1), and prior to dosing. Note: Rechecks of heart rate values will be permitted up to 2 times to confirm eligibility for study participation. Subjects may be eligible for participation in the study based on rechecked heart rate values if they fall within the ranges referenced above and if the PI (or designee), with agreement from the Celerion Medical Monitor and the Sponsor, feel that the results are not clinically significant, based on the age and renal impairment status of the subject, and will not impact study conduct.

12. Positive results for the urine or saliva drug screen at Screening or Check-in (Day -1), unless the positive drug screen is due to prescription drug use that is approved by the PI or designee, Celerion Medical Monitor, and Sponsor.

13. Positive results for urine or breath alcohol screen at Screening or Check-in (Day -1).

14. Positive results at Screening for human immunodeficiency virus (HIV), hepatitis B surface antigen (HBsAg), or hepatitis C virus (HCV). Subjects who are positive for hepatitis B virus, HCV, or HIV by antibody will require confirmation by polymerase chain reaction (PCR) before enrollment to detect presence of active virus. Subjects who are PCR positive will not be eligible.

15. Oral body temperature at Screening, Check-in (Day -1), and prior to dosing less than 35°C or greater than 37°C.

16. Is unable to refrain from or anticipates the use of any moderate or strong inhibitor or inducer of CYP3A4/A5, strong inhibitor of P-gp, proton pump inhibitors, antacids and H2-receptor antagonists from 14 days prior to dosing and through EOT or ET.

17. Has been on a diet incompatible with the on-study diet, in the opinion of the PI or designee, and as confirmed by the Celerion Medical Monitor and the Sponsor, within the 30 days prior to dosing and through EOT or ET.

18. Any medication (including over-the-counter) that would significantly alter eGFR, which, by the determination of the PI (or designee), and as confirmed by the Celerion Medical Monitor and the Sponsor, might interfere with the study (e.g., cimetidine) will be prohibited at least 2 weeks prior to dosing and through EOT or ET.

19. Donation of blood or significant blood loss within 56 days prior to dosing.
20. Plasma or platelet donation within 4 weeks prior to dosing.
21. Dosing in any other investigational study drug trial involving administration of any investigational drug in the past 30 days or 5 half-lives (if known), whichever is longer, prior to Check-in (Day -1).
22. Strenuous exercise within 5 days prior to Check-in (Day -1).
23. Poor peripheral venous access.
24. History of a major surgical procedure within 30 days prior to Screening.
25. History or presence, upon clinical evaluation, of any illness that, in the opinion of the Investigator, would interfere with the ability to provide informed consent or comply with study instructions, or that might confound the interpretation of the study results, or put the subject at undue risk.
26. Receipt of blood products within 2 months prior to Check-in (Day -1).

12.2.2 Additional Requirements for Subjects with RI

1. Has rapidly fluctuating renal function; or has demonstrated or suspected renal artery stenosis. Rapidly fluctuating renal function is defined as baseline and historical eGFR values that differ by more than 20% within at least 3 months for subjects with historical eGFR values available at the time of screening, or eGFR values that differ by more than 20% for the 2 screening measurements (\geq 14 days apart) for subjects with no historical eGFR values available at the time of screening.
2. Has had a renal transplant, a nephrectomy, or is a subject with a known history of nephrotic syndrome.
3. Unable to refrain from or anticipates the use of any medication or substance (including prescription or over-the-counter medications, vitamin supplements, natural or herbal supplements) from 14 days prior to dosing and through EOT or ET, unless it is a prescription or non-prescription medication used to treat manifestations of renal disease or medications needed to treat stable diseases which has been approved by the PI (or designee) with agreement from the Celerion Medical Monitor and the Sponsor, and provided they have been on a stable regimen for at least 30 days prior to dosing and are able to withhold use for 2 hours predose and 4 hours postdose on the day of dose administration (Day 1) unless approved by the PI (or designee), with agreement from the Celerion Medical Monitor, and Sponsor.
4. Has required new medication for renal disease within 30 days prior to Check-in (Day -1).
5. QT interval corrected for heart rate using Fridericia's method (QTcF) is $>$ 470 msec.

6. At-rest (i.e., supine for at least 5 minutes) diastolic blood pressure (BP) of < 50 or > 95 mmHg and/or systolic BP of < 89 or > 150 mmHg at Screening, Check-in, and prior to dosing. Out-of-range values that are not clinically significant (as determined by the PI or designee) may be repeated twice during Screening, Check-in (Day -1), and prior to dosing. Note: Rechecks of BP values will be permitted up to 2 times to confirm eligibility for study participation. Subjects may be eligible for participation in the study based on rechecked BP values if they fall within the ranges referenced above and the PI (or designee), with agreement from the Celerion Medical Monitor and the Sponsor, feels that the results are not clinically significant, based on the age and renal impairment status of the subject, and will not impact study conduct.

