The baseline eGFR will be obtained by taking the mean of the eGFR obtained from screening and from historical values within a 3-month period from screening. If no historical measurement is available, a second screening eGFR sample will be taken during the screening period (≥ 14 days apart) and the mean of the two values will be used as the Baseline eGFR for cohort assignment. Individual eGFR values recorded for each measurement contributing to the subject mean baseline value must fall within the specified eGFR ranges for each cohort (mild, moderate, and severe) to categorize subjects' renal impairment status.

6. Use of prescription and non-prescription medications that are needed to stabilize the subject's underlying medical condition (or concurrent baseline conditions) as deemed acceptable by the PI (or designee), with agreement from the Celerion Medical Monitor and the Sponsor, providing the subject has been on a stable dose for a minimum of 30 days prior to study drug administration.

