
* Estimated glomerular filtration rate (eGFR) based on Modification of Diet in Renal Disease (MDRD) equation at Screening. Baseline eGFR will be obtained for all subjects (i.e., subjects with RI and healthy-matched control subjects) by taking the mean of the eGFR obtained from Screening and from historical values within a 3-month period from Screening. If no historical measurement is available, a second Screening eGFR sample will be taken during the Screening period (≥ 14 days apart) and the mean of the two values will be used as the Baseline eGFR for cohort assignment. Individual eGFR values recorded for each measurement contributing to the subject mean baseline value must fall within the specified eGFR ranges for each cohort (i.e., healthy, mild, moderate, and severe) to categorize subjects' renal impairment status.
 
** For healthy-matched control subjects, a single assessment of actual creatinine clearance computed over a 24 hour urine collection may be used in place of the eGFR (based on the MDRD equation), at the Principal Investigator (PI)'s discretion.
		

Safety will be monitored throughout the study by repeated clinical and laboratory evaluations.

Subjects may be replaced at the discretion of the Sponsor.

Subjects will be housed in the clinical research unit (CRU) from Check-in (Day -1), at the time indicated by the CRU, until after completion of the Day 8 (End of Treatment [EOT]) or Early Termination (ET) study procedures. EOT is defined as the day on which the subject is released from the CRU, following all study procedures.

The CRUs will contact all subjects who received LOXO-292 (including subjects who terminate from the study early) at the End of Study (EOS,) by a follow up phone call (FU). The EOS/FU phone call will be performed 7 days (± 2 days) after the EOT visit or ET visit to determine if any study drug-related adverse event (AE) or serious adverse event (SAE) has occurred since the EOT or ET visit.

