6.7 Statistical Analysis of PK Parameters

6.7.1 Primary Analysis

A comparison of natural-log (ln)-transformed PK parameters (total: AUC0-t, AUC0-inf, and Cmax, and unbound: AUC0-t,u, AUC0-inf,u, and Cmax,u) will be made to evaluate the effect of renal function group on the PK of a single dose of LOXO-292. Since the comparison groups of subjects are independent in terms of degrees of RI and dependent based on the matching criteria, paired t-tests will be performed, using PROC TTEST of SAS®, to assess the differences in PK parameter between each hepatic impairment group versus the corresponding healthy matched control group with respect to 1 to 1 matching. Geometric mean ratios (GMRs) and ninety percent (90%) confidence intervals (CIs) for the ratios will be derived by exponentiation of the mean difference and the CIs obtained for the difference in mean between each renal function cohort and the matching healthy control group.

The paired t-test analysis for each PK parameter will be performed using the following SAS® code for each renal function cohort and its corresponding healthy matched control group:

CCI

CCI

RUN;

Programmer note: The paired t-test will be performed for each renal function group and the subset of corresponding healthy matched control subjects separately. LPKri refers to the set of ln-transformed PK parameters for the subjects in the renal impaired function group of interest (i.e., Mild, Moderate, or Severe) and LPKhealthy refers to the ln-transformed PK parameters for the set of corresponding matching healthy control subjects.

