6.7.3 Additional Analysis

The relationship between LOXO-292 PK parameters (i.e., Cmax and AUC, total and unbound) and measures of renal function (such as eGFR and CLcr) will be examined in an exploratory manner via a graphically linear regression approach. The PK parameters will be the dependent variable and show on y-axis and measurements for renal impairment will be independent variables and show on the x-axis. The regression equation with slope and intercept, the r-square, and the p-value for slope will be presented in the graphs as footnotes.

If data permits and judged necessary, an exploratory analysis will be performed to assess the relationship between LOXO-292 PK and renal impairment and the effect of covariates (age, BMI, and gender) using an appropriate approach.

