Appendix 16.2.4.4 Assessment of Renal Function (Safety Population)

Cohort	Site/ Subject Number	eGFR #1			eGFR #2			Creatinine clearance		
		Date	Time	Value (unit)	Date	Time	Value (Unit)	Mean eGFR (unit)	Date	Result (Unit)
XXXXX	XXX-XXX	DDMMYYYY	HH:MM	XXXXX	DDMMYYYY	HH:MM	XXXXX	XXXXXX	DDMMYYYY	XXXXX
	XXX-XXX	DDMMYYYY	HH:MM	XXXXX	DDMMYYYY	HH:MM	XXXXX	XXXXXX	DDMMYYYY	XXXXX
	XXX-XXX	DDMMYYYY	HH:MM	XXXXX	DDMMYYYY	HH:MM	XXXXX	XXXXXX	DDMMYYYY	XXXXX

Note: All subjects received a single oral dose of 160 mg LOXO-292 following a 2-hour fast.
Cohort Descriptions: <description>

CCI

DDMMYYYY HH:MM

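### The 20% renal-stability limit compares historical eGFR with a mean that already contains it, so one in-window historical value lets through a change of up to 40%

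*Protocol*

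**What the plan says.** Protocol 12.2.2 criterion 1 has two routes. For subjects with a historical value: "Rapidly fluctuating renal function is defined as baseline and historical eGFR values that differ by more than 20% within at least 3 months". For subjects without one, the test is "eGFR values that differ by more than 20% for the 2 screening measurements", taken at least 14 days apart.

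The term baseline is defined in Protocol 12.1.2 criterion 5: "The baseline eGFR will be obtained by taking the mean of the eGFR obtained from screening and from historical values within a 3-month period" before screening. The Synopsis, Sections 11.1 and 14.2.5, and SAP Section 3 ("by taking the mean of the eGFR obtained from Screening and from historical values within a 3-month period from Screening") say the same. Criterion 5 adds that each contributing measurement "must fall within the specified eGFR ranges for each cohort (mild, moderate, and severe").

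No passage names the denominator of the 20%. The time windows also differ: the exclusion criterion sets 3 months as a minimum, while the baseline definition sets it as a maximum.

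**The concern.** The historical value is compared with an average of which it is one half. That halves any real change before the 20% limit is applied, whereas the other route in the same sentence applies the limit to the full change. The same pair of eGFR values can therefore be eligible or ineligible depending only on whether the older value is labelled historical or screening.

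The criterion carries the protocol's numerical requirement for stable renal function. The revision history for Amendment 2 says a separate inclusion criterion on stable renal disease was dropped because this exclusion covers it. If the limit is not delivered, subjects whose function is moving can enter the mild, moderate or severe cohort. Their data then feed the primary comparison ("paired t-tests will be performed", SAP 6.7.1) and the ANCOVA (SAP 6.7.2), which have 8, 8 and 7 pairs in the mild, moderate and severe comparisons (SAP 16.1.9.2). The regression on eGFR is also affected, but it "will be examined in an exploratory manner via a graphically linear regression approach".

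**Working it through.** **Inputs.** Limit: 20% (Protocol 12.2.2 #1). Baseline with one in-window historical value: B = (S+H)/2 (12.1.2 #5). Ranges: mild 60 to <90, moderate 30 to <60 mL/min/1.73 m² (11.1). AUC0-t paired-difference SDs (SAP 16.1.9.2): mild 0.3774 (n=8), moderate 0.5311 (n=8), severe 0.5711 (n=7). Assumed, not in the documents: within-subject CV of 5–20%, lognormal error, and true eGFR uniform within the cohort range.

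**1. Two-sample route.** The two measurements are compared directly. With the percentage taken of the earlier value, the ratio of later to earlier must lie in 0.80–1.20. This route delivers the stated 20%.

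**2. Historical route.** B − H = (S+H)/2 − H = (S−H)/2.
- Percentage of H: |S−H|/(2H) ≤ 0.20, so |S−H|/H ≤ 0.40 and S/H lies in 0.60–1.40.
- Percentage of B: |S−H|/(S+H) ≤ 0.20, so S/H lies in 0.667–1.50.

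If several in-window historical values were averaged individually with S, the dilution would be greater. With two equal values, B − H = (S−H)/3 and the limit becomes 60% of H.

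**3. Adding the range rule, mild cohort.** Both values lie in 60 to <90, so S/H is strictly between 60/90 = 0.667 and 90/60 = 1.50.
- Percentage of B: the largest possible value approaches (90−60)/(90+60) = 20% and never reaches it. Nobody can be excluded.
- Percentage of H: for a fall, the largest value approaches (90−60)/(2×90) = 16.7%, so no fall can be excluded. A rise is excluded only if S > 1.4H with S < 90, that is, H below 90/1.4 = 64.3.

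Moderate and severe subjects can still be excluded under either denominator.

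**4. Examples.**
- H=88, S=62, both mild. Direct change 26/88 = 29.5%. B=75, so 13/88 = 14.8% (13/75 = 17.3% of B). Admitted on the historical route, excluded on the two-sample route.
- H=40, S=56, both moderate. Direct change 16/40 = 40%. B=48, so 8/40 = 20.0%, which does not exceed the limit: admitted.

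**5. Subjects with a true 30% fall, both true values in range.** Percentage admitted, with measured values also required in range and the percentage taken of H (simulation, 1 million draws):

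| Cohort | CV | Two-sample route | Historical route |
|---|---|---|---|
| Moderate | 5% | 2.9% | 87.4% |
| Moderate | 10% | 16.8% | 72.0% |
| Mild | 5% | 3.0% | 45.5% |
| Mild | 10% | 15.6% | 35.1% |

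With the percentage of B, the moderate historical-route figures are about 71% (CV 5%) and 57% (CV 10%). The severe cohort was not simulated.

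**6. Stable subjects.** Total screen failures including the range rule, percentage of H (simulation, 2 million pairs):

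| Cohort | CV | Two-sample route | Historical route |
|---|---|---|---|
| Mild | 10% | 38.9% | 33.5% |
| Mild | 15% | 57.0% | 49.1% |
| Mild | 20% | 69.1% | 61.7% |
| Moderate | 10% | 29.2% | 20.1% |
| Moderate | 15% | 47.4% | 31.5% |
| Moderate | 20% | 59.9% | 42.5% |

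**7. Precision if two pairs are dropped.** The 90% CI factor around the GMR is exp(t(0.95, n−1) × SD/√n), with the SD held fixed.
- Mild: exp(1.895 × 0.3774/√8) = 1.29; with n=6, 1.36.
- Moderate: 1.43; with n=6, 1.55.
- Severe: exp(1.943 × 0.5711/√7) = 1.52; with n=5, 1.72.

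**The case against.** The strongest reply is that baseline here was simply loose wording for the screening value. Criterion 5 of 12.1.2 opens by tying baseline eGFR to Screening, the second route compares individual measurements, and the superseded Amendment 1 text compared history with the screening value. On that reading both routes agree. It may well be what was intended, but the same criterion 5 goes on to define baseline as the mean, and every other section repeats that definition. A site following the current text literally applies the diluted test.

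Several other points stand:
- A historical value older than 3 months does not enter the mean, so it is not halved. The documents do not say how many subjects had in-window history.
- The range rule protects cohort assignment. The paired t-test and ANCOVA use cohort membership, not eGFR, and the cohorts already pool a 1.5-fold (mild) or 2-fold (moderate) span of eGFR. No bias in a GMR has been shown.
- The mild figures for a 30% fall apply only where H is at least 60/0.7 = 85.7, about 14% of the mild range ((90−85.7)/30).
- The investigator, medical monitor and sponsor review all screening data, and new renal medication within 30 days is excluded. Neither safeguard sets a numerical limit on eGFR change.

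These limit the consequence. They do not make the criterion deliver 20%.

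**Conclusion.** The point holds. As written, with one historical value inside the 3-month window, the stated 20% limit operates as 40% of H, or as S/H from 0.667 to 1.50 if the percentage is of baseline. In the mild cohort the historical-route eGFR test excludes nobody under the baseline denominator and no falling subject under the other. The algebra needs no assumption beyond the protocol's own definition of baseline. The admission and screen-failure rates rest on the assumed CVs and uniform eGFR.

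This should be corrected, but it does not by itself undermine the results. The residual risk is renally impaired subjects whose function moved by 20–40% within their cohort before dosing, in comparisons small enough for one or two subjects to matter. Whether any were enrolled cannot be told from the documents.

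**What to change.** 1. Reconcile Protocol 12.1.2 criterion 5 with 12.2.2 criterion 1 so that both routes apply the protocol's existing 20% limit to two individual eGFR measurements, with one time window and a named denominator.
2. For subjects already enrolled, use SAP Appendix 16.2.4.4, which lists both eGFR values with dates, to count renally impaired subjects whose two values differ by more than 20%. If there are none, say so in the CSR.
3. If there are any, repeat the paired t-test (SAP 6.7.1) and the ANCOVA (SAP 6.7.2) without them, labelled post hoc because outputs dated 30APR2020 already exist.

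The cost is a wording correction, a count from a planned listing and at most one sensitivity run. For any further screening, the direct comparison raises failures among stable subjects on the historical route by about 5 points (mild) and 9 points (moderate) at CV 10%, and by 8 and 16 points at CV 15%. The sensitivity run loses pairs and so precision, as shown in step 7 of the working.
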